### 12.4.2 Methods for Secondary Endpoints

Secondary endpoints will be evaluated based on the treated population.

Time to event distribution will be estimated using Kaplan Meier techniques. This will be done for PFS. Median PFS along with 95% CI will be constructed based on a log-log transformed CI for the survivor function. Rates at fixed time points (e.g., PFS at 6 and 12 months) will be derived from the Kaplan Meier estimate and corresponding confidence interval will be derived based on Greenwood formula for variance derivation and on log-log transformation applied on the survivor function.

The DCR will be summarized for subjects who achieve confirmed PR or CR using the Kaplan-Meier (KM) product-limit method. Median values of DCR, along with

95% CI will be constructed based on a log-log transformed CI for the survivor function.

The DOR will be summarized for subjects who achieve confirmed PR or CR using the Kaplan-Meier (KM) product-limit method. Median values of DOR, along with 95% CI will be constructed based on a log-log transformed CI for the survivor function.

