### 12.2 Sample Size/Accrual Rate

The optimal two-stage design to test the null hypothesis that  $P \leq 0.050$  versus the alternative that  $P \geq 0.150$  has an expected sample size of 29.51 and a probability of early termination of 0.736. If the regimen is actually not effective, there is a 0.097 probability of concluding that it is (the target for this value was 0.100). If the regimen is actually effective, there is a 0.199 probability of concluding that it is not (the target for this value was 0.200). After testing the drug on 20 patients in the first stage, the trial will be terminated if 1 or fewer respond. If the trial goes on to the second stage, a total of 56 patients will be studied. If the total number responding is less than or equal to 4, the regimen is rejected.

Assuming a 15% screening failure rate, it is estimated that approximately 64 subjects will be enrolled in order to achieve 56 treated subjects.

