### 12.3.2 Secondary Endpoints

Secondary endpoints include safety and tolerability of study treatment; PFS, DCR, DOR and OS in the all treated subjects population.

Safety and tolerability objectives will be measured by the incidence of adverse events, serious events, deaths, and laboratory abnormalities. Dates and duration of study treatment delays will also be described.

PFS is defined as the time from first dose to the date of the first documented tumor progression (per RECIST 1.1), or death due to any cause. Clinical deterioration in the absence of radiographic evidence is not considered progression for purposes of determining PFS. Subjects who die without a reported prior progression will be considered to have progressed on the date of their death. Subjects who did not progress or die will be censored on the date of their last evaluable tumor assessment.

Subjects who did not have any on study tumor assessments and did not die will be censored on the first dosing date. Subjects who started any palliative local therapy or subsequent anti-cancer therapy without a prior reported progression will be censored at the last evaluable tumor assessment prior to initiation of the palliative local therapy or subsequent anti-cancer therapy, whichever procedure occurred first. PFS rate at 6 months is defined as the rate from Kaplan-Meier estimate 6 months after first dosing date.

Disease control rate is defined as the number of subjects with a BOR (per RECIST v1.1 criteria) of confirmed CR or PR or SD (stable disease), divided by the number of treated subjects.

Duration of response will be summarized among subjects with objective response in and is measured from the time at which the criteria for objective response are first met until the date of a progression event (according to the definition of PFS). Subjects with objective response who does not have a progression event will be censored at the same time they were censored under the definition of PFS.

Overall survival is defined as the time from first dosing date to the date of death. A subject who has not died will be censored at last known alive date. The overall

survival rate at 6 months is the rate from Kaplan-Meier estimate 6 months after dosing date.

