### 12.3.3 Exploratory Endpoint(s)

All biomarker measures, T-cell response, immune phenotype and inflammatory response evaluation will be listed, tabulated, and where appropriate plotted. Tumor tissue IHC, functional analysis and genomic analysis will be listed, tabulated and where appropriate plotted. For the continuous data, summary statistics and the corresponding changes (or percent changes) from baseline will be provided at each time-point of assessment as well as for the changes from baseline to the peak value. Categorical data will be summarized as appropriate. Subjects will be grouped by dose level or clinical response. As this is an open-label study without a control treatment, statistical analyses will be done to aid in the understanding of the results. The associations of biomarkers with dose, clinical response, or time-to-event endpoints may be assessed using the appropriate statistical methods (analysis of variance [ANOVA], categorical, or survival model), depending on the endpoint. Correlation of baseline expression levels or changes in expression levels with response or time-to-event endpoints will identify potential responsive (or resistant) subgroups.

The ctDNA and IMG objectives will be measured from serum concentration. Response characteristics will be summarized descriptively and are further described in the statistical analysis plan.

Other exploratory endpoints are discussed in details in the statistical analysis plan.

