## 12.4 Efficacy Analyses

### 12.4.1 Methods for Primary Endpoints

Among all treated subjects, the ORR will be summarized by binomial response rates and their corresponding two-sided 95% exact CIs using Clopper-Pearson method. The null hypothesis will be rejected if the 2-sided 95% CI lower bound for the ORR radiology assessed estimate is greater than 15%.

To further characterize the response: time to objective response, depth of response and BOR by response category will be summarized using descriptive statistics.

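### Section 12.4.2 analyses disease control rate as a Kaplan-Meier median in confirmed responders, which cannot return the proportion of all treated subjects defined in section 12.3.2

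*Combined protocol and SAP*

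**What the plan says.** Section 1.2.3 names DCR among the secondary efficacy objectives. Section 12.3.2 defines it: "Disease control rate is defined as the number of subjects with a BOR (per RECIST v1.1 criteria) of confirmed CR or PR or SD", over the number of treated subjects. The same section places DCR, with the other secondary endpoints, in the all-treated population.

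Section 12.4.2 opens by putting the secondary endpoints in the treated population. Its DCR paragraph then reads "The DCR will be summarized for subjects who achieve confirmed PR or CR using the Kaplan-Meier (KM) product-limit method" and asks for a median DCR with a 95% interval from the log-log transformed survivor function. The next paragraph reads "The DOR will be summarized for subjects who achieve confirmed PR or CR using the Kaplan-Meier (KM) product-limit method" and continues in the same way. For DOR the restriction to responders agrees with 12.3.2: "Duration of response will be summarized among subjects with objective response".

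Two other places bear on the point. For ORR, section 12.4.1 says "Among all treated subjects, the ORR will be summarized by binomial response rates and their corresponding two-sided 95% exact CIs using Clopper-Pearson method". It also says that "depth of response and BOR by response category will be summarized using descriptive statistics".

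**The concern.** The definition and the analysis method describe different quantities. The definition is a single proportion in everyone treated, with SD counted as success. The method is a survival-type median in confirmed responders, a group that contains no SD subjects.

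An analyst who follows 12.4.2 could in effect report DOR a second time under the DCR label. An analyst who goes back to 12.3.2 gets the right point estimate but finds no stated interval method and would have to choose one, possibly after seeing the data. The trial is open-label and single-arm, and section 11.1.7 plans no central radiology review, so the method is better fixed in advance.

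**Working it through.** **1. The two rules side by side**

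| | Definition (12.3.2) | Method (12.4.2) |
|---|---|---|
| Population | All treated subjects | Confirmed CR or PR only |
| Counted as success | Confirmed CR or PR, and SD | No success count; SD subjects are not in the set |
| Type of quantity | Proportion | Median from a survivor function |
| Time origin, event, censoring | Not needed | Needed, but not given for DCR |

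With r confirmed responders, s subjects with SD and N treated, the definition gives DCR = (r + s)/N. Restricted to the set in 12.4.2, the same ratio is r/r = 100%, whatever s and N are. A Kaplan-Meier median in that set would have to be a time. Section 12.3.2 supplies the origin, event and censoring rules for PFS, DOR and OS, but no section supplies them for DCR.

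**2. Text comparison**

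The DCR paragraph has two sentences and 40 words. Replacing DCR with DOR gives the next paragraph exactly. That it was duplicated is an inference from this match; the documents do not say so.

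**3. Size of the set named in 12.4.2**

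Inputs from section 12.2: 20 patients in stage 1, 56 in total, null and alternative response rates 5% and 15%, and the stopping rule "After testing the drug on 20 patients in the first stage, the trial will be terminated if 1 or fewer respond".

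The plan's own figures come first. With X the number of responders in stage 1:

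- P(X ≤ 1 | n = 20, p = 0.05) = 0.95^20 + 20 × 0.05 × 0.95^19 = 0.3585 + 0.3774 = 0.736, as stated in 12.2.
- Expected sample size = 20 + (1 − 0.7358) × 36 = 29.51, as stated.
- At p = 0.15: 0.85^20 + 20 × 0.15 × 0.85^19 = 0.0388 + 0.1368 = 0.176.

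Expected responders if the trial continues are E[X | X ≥ 2] + 36p, where E[X | X ≥ 2] = (20p − P(X = 1)) / (1 − P(X ≤ 1)):

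- p = 0.05: (1 − 0.3774)/0.2642 = 2.357; plus 1.8 gives 4.16.
- p = 0.15: (3 − 0.1368)/0.8244 = 3.473; plus 5.4 gives 8.87.

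Share of the 56 treated subjects outside the set:

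- p = 0.05: (56 − 4.16)/56 = 51.84/56 = 92.6%.
- p = 0.15: (56 − 8.87)/56 = 47.13/56 = 84.2%.

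The central 90% range of the number of responders, given continuation, is 2 to 7 at 5% and 5 to 13 at 15%. If the trial stops at stage 1, the set holds 0 or 1 subject, so a median with an interval is not usable.

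**4. What the defined endpoint would give**

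The documents state no expected DCR, so a range is assumed. Exact Clopper-Pearson 95% intervals:

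| Assumed DCR | N = 56 | N = 20 (stop at stage 1) |
|---|---|---|
| 25% | 14/56: 14.4% to 38.4% | 5/20: 8.7% to 49.1% |
| 50% | 28/56: 36.3% to 63.7% | 10/20: 27.2% to 72.8% |
| 75% | 42/56: 61.6% to 85.6% | 15/20: 50.9% to 91.3% |

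**The case against.** The strongest reply is that this is a drafting slip of little consequence. The numerator and denominator are clear in 12.3.2, the opening line of 12.4.2 repeats the treated population, and the BOR table in 12.4.1 would let anyone add up the point estimate. What is missing is an interval for one descriptive endpoint, and a median DCR would probably be queried before it was reported. This stands as a limit on the weight of the point. It does not remove the contradiction, because 12.4.2 states a rule and that rule gives the wrong quantity.

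It is also fair to say that the paragraph cannot be executed as written, since it has no time variable. Repeating DOR is therefore a likely outcome of following it, not a certain one.

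The percentages in the working measure the size of the responder set and would apply equally to the DOR paragraph, where the restriction is correct. They are not an error in a reported DCR. The 0-or-1 figure assumes that accrual halts at exactly 20 and that no later response is counted.

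Finally, section 12.3.3 says "Response characteristics will be summarized descriptively and are further described in the statistical analysis plan". That sentence concerns exploratory endpoints, and no separate plan is among the documents supplied. If one exists and covers DCR, the missing interval may be settled there, but 12.4.2 would still contradict 12.3.2.

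**Conclusion.** The concern holds. As written, 12.4.2 cannot return the DCR defined in 12.3.2, and it conflicts with its own opening line on population. Nothing else in the documents supplied repairs it: the BOR summary gives a point estimate at most, and no interval for the proportion is planned.

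Among the subjects left out, those with SD are wrongly missing from both numerator and denominator; progressors and non-evaluable subjects are wrongly missing from the denominator only. The documents give no SD rate, so that split, and hence the distortion of a reported DCR, cannot be derived. The set sizes rest on the design response rates of 5% and 15% and on confirmed responses being the ones counted at the stage 1 look.

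The point should be fixed before the analysis but is confined to a descriptive secondary endpoint with no hypothesis test. The ORR analysis, the sample size and the stopping rule are not affected.

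**What to change.** Replace the DCR paragraph in 12.4.2 with: *DCR, as defined in section 12.3.2, will be summarized among all treated subjects as a binomial proportion with a two-sided 95% exact (Clopper-Pearson) confidence interval.* Keep the Kaplan-Meier text for DOR only.

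Another interval for a proportion would also resolve the conflict. Clopper-Pearson is proposed because the plan already uses it for ORR in the same population.

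It would help to add to 12.3.2 that confirmation applies to CR and PR and that SD is assigned according to Table 5, since the present wording leaves unclear whether SD must also be confirmed.

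The cost is one replaced paragraph, and optionally one added sentence, before the analysis. No new data and no change to the sample size are needed.

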#### 12.4.3 Safety Analyses

Safety analysis will be performed in all treated subjects. Descriptive statistics of safety will be presented using National Cancer Institute (NCI) Common Terminology Criteria for Adverse Events (CTCAE) version 4.0. All on-study AEs, drug-related AEs, SAEs and drug-related SAEs, AEs and drug-related AEs leading to drug discontinuation will be tabulated using worst grade per NCI CTCAE v 4.0 criteria by system organ class and preferred term, based on MedDRA terminology. On-study lab parameters including hematology, coagulation, chemistry, liver function and renal function will be summarized using worst grade per NCI CTCAE v 4.0 criteria.

Frequency, management and resolution of IMAEs will be analyzed. A tabular summary of the incidence of overall IMAEs (by preferred term) and serious IMAEs will be performed. A descriptive analysis of IMAEs including time-to-onset, severity, duration, action taken with the study drug, dosing delays of the study drug, corticosteroid details, re-challenge information and outcome of the AE will be individually characterized by IMAE category ([Section 6.6.1](#)).

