3.1.7 ECOG performance status  $\leq 1$  (see Appendix 1)

3.1.8 Prior palliative radiotherapy to non-CNS lesions must have been completed at least 2 weeks prior to treatment. Subjects with symptomatic tumor lesions at baseline that may require palliative radiotherapy within 4 weeks of first treatment are strongly encouraged to receive palliative radiotherapy prior to treatment.

3.1.9 Patients must have normal organ and marrow function as defined below:

- WBC	$\geq 1,500/\text{mcL}$
- absolute neutrophil count	$\geq 1,000/\text{mcL}$
- hemoglobin	$\geq 8.0 \text{ g/dL}$
- platelets	$\geq 75,000/\text{mcL}$
- total bilirubin	$\leq 1.5 \times \text{institutional ULN}$ (patients with Gilbert's syndrome may have serum bilirubin $\leq 3 \times \text{ULN}$ )
- AST/ALT	$\leq 3 \times \text{institutional ULN}$ ( $\leq 5 \times \text{ULN}$ in the presence of liver metastases)
- creatinine	$\leq 1.5 \times \text{institutional ULN}$ or creatinine clearance (CrCl) $\geq 40 \text{ mL/min}$ (if using the Cockcroft-Gault formula below):

*Female:*

$$\text{CrCl} = \frac{(140 - \text{age in years}) \times \text{weight in kg} \times 0.85}{72 \times \text{serum creatinine in mg/dL}}$$

*Male:*

$$\text{CrCl} = \frac{(140 - \text{age in years}) \times \text{weight in kg} \times 1.00}{72 \times \text{serum creatinine in mg/dL}}$$

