## 6. ADVERSE EVENTS: LIST AND REPORTING REQUIREMENTS

This study will use the descriptions and grading scales found in the revised National Cancer Institute Common Terminology Criteria for Adverse Events (CTCAE) Version 4.0 for adverse event reporting that can be found at [http://ctep.cancer.gov/protocolDevelopment/electronic\\_applications/ctc.htm](http://ctep.cancer.gov/protocolDevelopment/electronic_applications/ctc.htm).

Information about all AEs, whether volunteered by the subject, discovered by investigator questioning, or detected through physical examination, laboratory test or other means, will be collected, recorded, and followed as appropriate.

All AEs and SAEs experienced by subjects will be collected and reported from the first dose of nivolumab, throughout the study, and will only be followed for 4 weeks unless related to the investigational agent. All SAEs will be collected for 100 days after the last dose of nivolumab. Subjects who have an ongoing AE related to the study procedures and/or medication(s) may continue to be periodically contacted by a member of the study staff until the event is resolved or determined to be irreversible by the investigator.

**Laboratory abnormalities:** Laboratory abnormalities present at the screening visit will be recorded as pre-treatment signs and symptoms. After study treatment administration, all grade 3 and 4 clinical laboratory results that represent an increase in severity from baseline will be reported as adverse events. A grade 1 or 2 clinical laboratory abnormality should be

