## 6.1 Definitions

### 6.1.1 Adverse Event

An adverse event (AE) is defined as any new untoward medical occurrence or worsening of a preexisting medical condition in a clinical investigation subject administered study drug and that does not necessarily have a causal relationship with this treatment. An AE can therefore be any unfavorable and unintended sign (such as an abnormal laboratory finding), symptom, or disease temporally associated with the use of study drug, whether or not considered related to the study drug.

BMS will be reporting adverse events to regulatory authorities and ethics committees according to local applicable laws including European Directive 2001/20/EC and FDA Code of Federal Regulations 21 CFR Parts 312 and 320.

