## 9. STUDY CALENDAR

	Screening (0-28 day pre-dose)	Cycle 1			Cycle 2, 3, etc.			End of Treatment (EOT) Assessment n	Follow-Up Visit 30 days post EOT/ 90 days post EOT	Survival/ FU visits l
		D1	D15	D29	D1	D15	D29			
CLINICAL ASSESSMENTS										
Informed consent	X									
Inclusion/Exclusion Criteria	X									
Demographics	X									
Medical history	X									
Physical exam o	X	X	X	X	X	X	X	X	X	
Vital signs, Height (baseline), Weight, O 2 Sat	X	X	X	X	X	X	X	X		
Height (baseline), Weight, O 2 Sat	X	X	X	X	X	X	X	X		
ECOG performance status	X	X	X	X	X	X	X	X	X	
CBC w/diff, plts	X	X f	X f	X f	X f	X f	X f	X	X	
Serum chemistry a	X	X f	X f	X f	X f	X f	X f	X	X	
Hepatitis Panel b	X									
TSH, Free T4, Free T3 c	X				X			X		
EKG	X	X f								
Urinalysis	X									
Pregnancy Test (WOCBP only) d	X	X			X					
Tumor Assessment/Imaging e	X				X				X m	
TREATMENT										
Nivolumab		X g	X g	X g	X g	X g	X g			
Ipilimumab		X g			X g					
CORRELATIVE STUDIES										
Archival Tumor h	X									
Fresh Tumor Biopsy i (Second stage only)	X				X					
Plasma for Immunogenecity Studies (Second stage only) j		X	X	X	X				X	
Plasma for ctDNA (Second stage only) j		X	X	X	X				X	
OTHER ASSESSMENTS										
Concurrent meds	X	X	X	X	X	X	X	X	X	
Symptom/Toxicity Assessment j	X	X	X	X	X	X	X	X	X	

Survival Status/Subsequent Therapy									X

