	
a: LDH, AST, ALT, ALP, T. bili, BUN or serum urea level, creatinine, albumin, Ca, Mg, Na, K, Cl, phosphate, glucose, amylase, lipase, TSH, Free T4, Free T3, within 14 days prior to first dose.
 
b: Hep B/C (HBV sAg, HCV antibody or HCV RNA), within 28 days prior to first dose.
 
c: Thyroid Function Testing to be evaluated every 6 weeks
 
d: A serum or urine pregnancy testing is required prior to study enrollment/registration, also within 24 hours prior to D1 (and extension to 72 hours may be granted if unable to obtain within 24 hrs). Must be reassessed every 4 weeks.
 
e: CT scan of the chest and other relevant sites as well as MRI brain with gadolinium (or CT scan brain with contrast if MRI is contraindicated) will be performed <math>\leq</math> 4 weeks prior to the start of therapy. For subsequent scans, may be done within +/- 7 days of intended visit.
 
f: Within 72 hrs prior to dosing to include CBC w/ differential, AST, ALT, ALP, T. bili, BUN or serum urea level, creatinine, albumin, Ca, Mg, Na, K, Cl, LDH, phosphate, glucose, amylase, lipase, TSH (with reflexive Free T4 and Free T3). Note: C1D1 labs do not need to be repeated if they were performed within 14 days of dosing.
 
g: All treatments may be performed +/- 2 days of the intended treatment administration dates schedule for all cycles.
 
h: Recent sample or archival obtained. One (1) formalin-fixed paraffin embedded tumor tissue block or a minimum of 10 unstained tumor tissue sections are acceptable.
 
i: Mandatory fresh tissue will be collected for biomarker studies at baseline and on treatment (week 6-8) for patients enrolled in the second stage of the study.
 
j: Immunogenecity samples should be collected just before the administration of the first drug (preferably within 30 minutes).
 
k: Adverse event evaluation as per Common Terminology Criteria for Adverse Events (CTCAE) version 4.0
 
l: Survival follow-up may be done via phone call for survival status and subsequent therapy
 
m: CT if the subject came off study for reasons other than PD
 
n: EOT assessments do not need to be repeated if performed within 14 days
 
o: In order to minimize the need for research-only in-person visits, telemedicine visits may be substituted for in-person clinical trial visits or portions of clinical trial visits where determined to be appropriate and where determined by the investigator not to increase the participant's risks. Prior to initiating telemedicine for study visits the study team will explain to the participant, what a telemedicine visit entails and confirm that the study participant is in agreement and able to proceed with this method. Telemedicine acknowledgement will be obtained in accordance with the Guidance for Use of Telemedicine in Research. In the event telemedicine is not deemed feasible, the study visit will proceed as an in-person visit. Telemedicine visits will be conducted using HIPAA compliant method approved by the Health System and within licensing restrictions.
								

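### The laboratory summary in 12.4.3 takes the worst on-study grade without reference to baseline, so abnormal entry values that never change are counted as on-study abnormalities

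*Combined protocol and SAP*

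**What the plan says.** Section 12.4.3 (Safety Analyses) gives one sentence to laboratory data: "On-study lab parameters including hematology, coagulation, chemistry, liver function and renal function will be summarized using worst grade per NCI CTCAE v 4.0 criteria". The analysis set is all treated subjects.

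This summary is part of how a secondary objective is measured. Section 12.3.2 states: "Safety and tolerability objectives will be measured by the incidence of adverse events, serious events, deaths, and laboratory abnormalities". Laboratory abnormalities stand there as an item separate from adverse events.

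Eligibility section 3.1.9 does not require normal values, despite its introductory wording. AST and ALT may be up to 3 x ULN, or up to 5 x ULN "in the presence of liver metastases". Bilirubin may be up to 1.5 x ULN (3 x ULN in Gilbert's syndrome), hemoglobin as low as 8.0 g/dL, platelets as low as 75,000/mcL and neutrophils as low as 1,000/mcL. Creatinine must be within 1.5 x ULN or clearance at least 40 mL/min.

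Elsewhere the plan does use baseline. Section 6 says: "Laboratory abnormalities present at the screening visit will be recorded as pre-treatment signs and symptoms", and, for the period after treatment starts, "all grade 3 and 4 clinical laboratory results that represent an increase in severity from baseline will be reported as adverse events". Section 6.1.1 defines an adverse event as "any new untoward medical occurrence or worsening of a preexisting medical condition".

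On which tests are done, the study calendar (Section 9) has a hematology row, "CBC w/diff, plts", and a serum chemistry row. Footnote a lists the chemistry panel as "LDH, AST, ALT, ALP, T. bili, BUN or serum urea level, creatinine, albumin, Ca, Mg, Na, K, Cl, phosphate, glucose, amylase, lipase", followed by thyroid tests. Footnote f gives a similar pre-dose panel with the blood count.

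**The concern.** A worst-grade summary answers how abnormal a subject ever was on study. A safety reader wants to know how much changed after treatment began. The two agree only if everyone starts at grade 0, and the eligibility criteria do not ensure that. A subject with liver metastases who enters with AST at 4 x ULN and stays there throughout would be counted in the on-study liver summary although nothing happened.

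In a randomised trial the control arm would show the background rate of such abnormalities. This trial has one arm, so the laboratory table has to be interpretable alone. Without baseline, its liver and hematology rows mix disease or prior-treatment effects with change on study. It would also count subjects on a different basis from the grade 3-4 laboratory adverse events collected under Section 6.

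There is a smaller mismatch as well: coagulation is among the groups to be summarised, but no coagulation test appears in the schedule.

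**Working it through.** The plan states no figure on this point, so there is none to reproduce. The check is a comparison of sections, followed by an illustration under assumed rates.

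**Comparison of sections**

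1. *Can a subject carry a graded abnormality at entry?* Yes. Section 3.1.9 admits values outside normal limits. Section 5.2.3 refers to subjects with Grade 1 AST/ALT or total bilirubin at baseline and to a 2-grade shift from there. So the plan expects some subjects to start above grade 0, and grades are not measured relative to each subject's own baseline.
2. *Does the laboratory sentence in 12.4.3 remove such values?* No. It takes the worst on-study grade, and an unchanged abnormal value keeps its grade.
3. *Does another section supply a baseline rule for this table?* None was found. The Section 6 rule governs what is reported as an adverse event. Change from baseline appears in 12.3.3, but for continuous biomarker data only.
4. *Are baseline values available?* Yes. Hematology and chemistry are drawn at screening and before dosing (Section 9, footnotes a and f).
5. *Is coagulation scheduled?* No. Neither the calendar rows nor footnotes a and f contain such a test. Section 4.2.2.3 permits full-dose anticoagulation, so any unscheduled values could come from a selected group and reflect co-medication.

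**Illustration (assumed rates)**

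Inputs: N = 56, the full two-stage sample in 12.2; b, the assumed share entering with an abnormality in one parameter that persists; t, the assumed true rate of new or worsened abnormality, taken as equal in all subjects.

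- Counted by worst on-study grade (any grade): N x [b + (1 - b) x t]
- Counted as new or worsened: N x t
- Excess: N x b x (1 - t)

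| b | Worst-grade count, t = 10% | Worst-grade count, t = 20% |
|---|---|---|
| 10% | 10.6 (19%) | 15.7 (28%) |
| 20% | 15.7 (28%) | 20.2 (36%) |
| 30% | 20.7 (37%) | 24.6 (44%) |
| 40% | 25.8 (46%) | 29.1 (52%) |
| New or worsened, any b | 5.6 (10%) | 11.2 (20%) |

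For example, with b = 10% and t = 10%: 56 x (0.10 + 0.90 x 0.10) = 56 x 0.19 = 10.6, against 56 x 0.10 = 5.6, an excess of 56 x 0.10 x 0.90 = 5.0 subjects.

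The percentages do not depend on N, so they also apply if the trial stops after 20 patients. If b = 0 the two counts coincide. If some entry abnormalities resolve before the first on-study value, the excess is smaller.

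**The case against.** A reader might infer that the plan reports pre-existing abnormalities as toxicity. The documents do not support that:

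- Screening abnormalities are recorded as pre-treatment findings, grade 3-4 laboratory results are reported as adverse events when they have worsened from baseline (Section 6), and an adverse event must be new or worsening (6.1.1). The AE, drug-related AE, SAE and discontinuation tables in 12.4.3 draw on those definitions.
- The transaminase and bilirubin terms under hepatitis in 6.6.1 count as immune-mediated events only if immunosuppressive medication was given.
- Potential drug-induced liver injury in 6.5.3 requires that no other cause, including pre-existing liver disease, is apparent.

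A subject with stable, untreated AST at 4 x ULN would enter none of these. This stands in full, and it limits the point to the laboratory table. The Section 6 rule for grade 1-2 results breaks off in the text available, so nothing is concluded about it.

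The other side can add that the table is descriptive, that 12.4.3 does not forbid showing baseline grade beside it, and that no decision rule depends on it. All true. But following the sentence as written gives the table described, and 12.3.2 names laboratory abnormalities as a safety measure in their own right. Section 12.3.3 refers to a statistical analysis plan for further detail, but for response characteristics and exploratory endpoints, not for safety laboratory data.

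On coagulation, a reader might infer that it is never measured. The text supports only that it is not scheduled; unscheduled clinical tests remain possible.

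**Conclusion.** The point holds for the laboratory table. As written, 12.4.3 would count subjects with unchanged entry abnormalities among those with on-study abnormalities, because it does not carry forward the baseline rule of Section 6. AE, SAE, immune-mediated event and liver-injury reporting is not shown to be affected, and the primary endpoint and sample size are untouched.

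The size cannot be stated. The documents give no prevalence of abnormal values at entry, and the range shown (19% to 46% against a true 10%; 28% to 52% against a true 20%) follows entirely from assuming that 10% to 40% of subjects enter with an abnormality that persists. It applies to an any-grade count for one parameter. Nothing here shows that a permitted entry value would put a subject in a grade 3-4 row, and a reader should not infer a specific number of misclassified subjects.

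The coagulation mismatch is real but minor: a summary is planned for which no test is scheduled.

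**What to change.** In 12.4.3, present a baseline-to-worst-grade shift table for each laboratory parameter, and report the proportion of treated subjects whose grade worsened from baseline. Define baseline as the last value before the first dose, from the screening or pre-dose samples, and show subjects with no baseline value as a separate row. The worst-grade summary can stay beside it. This brings the table into line with the Section 6 rule.

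Reconcile coagulation between 12.4.3 and Section 9, for example by removing it from the planned summary or by labelling any values as unscheduled.

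The cost is a sentence or two of analysis text and one additional standard table. The shift table needs no new samples or visits, because the baseline values are already collected.
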